11.3 The Level of Statistical Significance

Alpha error of 5%, beta error 20%, power 80%

11.4 Criteria for the Termination of the Trial.

The trial will be terminated when 10 non-pregnant volunteers and 30 post natal volunteers have completed the study protocol.

11.5 Procedure for Accounting for Missing, Unused, and Spurious Data.

The trial will be terminated once we have 40 complete data sets. There will be no unused data sets. Spurious data will be excluded from analysis and will require additional recruitment.

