4. BACKGROUND AND RATIONALE

Patient safety agencies such as the National Patient Safety Agency (NPSA) and European Medicines Agency recommend adoption of equipment that prevents wrong route drug administration¹. For example medicine intended for the intravenous route should not be possible to be given via the epidural route, hence limiting potentially catastrophic complications associated with human error². However, the epidural blood patch requires equipment that connects to the intravenous and epidural route, as blood is taken from a patient's vein and then it is injected into the patient's epidural space for therapeutic effect. Hence equipment is required that allows blood aspiration from the patient but does not have the potential to inject into the patient hence complying with patient safety agency recommendations. Aspirating blood from the patient via a non-Luer one-way filter valve has the theoretical potential of activating the clotting cascade. If this occurred it could reduce the time the clinician has to utilise the blood before it clots in the syringe. Changes in clotting characteristics also has unknown implications when injected into the epidural space with regards to the therapeutic effect of the procedure.

The epidural blood patch is mainly used in obstetric anaesthesia in the treatment of dural puncture headaches, however it is also used to treat conditions such as spontaneous intracranial hypotension, hence this study involves post natal and non-pregnant populations. This study requires blood to be taken from the study participants via a venepuncture. This will require 12mls of blood to be taken from the patient via a standard 21G hypodermic needle and also 2mls of blood via the new 21G non-Luer one-way filter valve needle. The blood will undergo clotting profile testing. The implications for study subjects would be two venepunctures and a total of 14mls of blood taken. The post natal population would only require one additional venepuncture with the new one-way valve needle as they would already be having bloods taken for their day 2 post elective cesarean section bloods, an additional 9ml of blood only.

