8.6 Definition of End of Trial

The end of trial will be the completion of the 30th paired TEG test in the pregnant group and the 10th in the volunteer group.

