8.7 Discontinuation/Withdrawal of Participants from Study Treatment

Each participant has the right to withdraw from the study at any time. In addition, the investigator may discontinue a participant from the study at any time if the investigator considers it necessary for any reason including:

Ineligibility (either arising during the study or retrospective having been overlooked at screening)

Significant protocol deviation

Significant non-compliance with treatment regimen or study requirements

An adverse event which requires discontinuation of the study or results in inability to continue to comply with study procedures

Developing a medical condition

Consent withdrawn

Lost to follow up

If participants are withdrawn from the study they will be replaced and data acquired from withdrawn participants will be destroyed. The reason for withdrawal will be recorded in the CRF.

If the participant is withdrawn due to an adverse event, the investigator will arrange for follow-up visits or telephone calls until the adverse event has resolved or stabilised.

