11. STATISTICS

11.1 Description of Statistical Methods

The primary outcome for this study is change in time to initiate clot formation, as measured by the R time using thromboelastography. As subjects are to be exposed to both study limbs the data collected will be analysed using paired tests for statistical differences. The variation is different for non-pregnant and post natal subjects, therefore we have calculated sample size for each of the two study populations separately. As the sample size is small it is unlikely that the results will be normally distributed, therefore non-parametric test will be employed. As the sample sizes are small we do not anticipate needing any interim analysis. There is no plan to compare non-pregnant and post natal groups, only the within group differences.

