11.7 Inclusion in Analysis

All evaluable patient data will be analysed to a total of 10 non-pregnant and 30 post natal participants have completed the intervention arms of the study.

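### The replace-until-complete rule leaves a sample that clots before TEG loading unrecorded and unanalysed, which biases the R-time comparison if such losses differ between the needles

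*Combined protocol and SAP*

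**What the plan says.** Section 11.1 sets the endpoint: "The primary outcome for this study is change in time to initiate clot formation, as measured by the R time using thromboelastography". The comparison is within participant, and because the samples are small a "non-parametric test will be employed"; the test is not named.

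Four sections decide which participants supply data:

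- Section 8.6 ends the trial on "completion of the 30th paired TEG test in the pregnant group and the 10th in the volunteer group".
- Section 11.5 stops on complete data sets ("The trial will be terminated once we have 40 complete data sets. There will be no unused data sets") and adds: "Spurious data will be excluded from analysis and will require additional recruitment".
- Section 11.7 restricts the analysis: "All evaluable patient data will be analysed to a total of 10 non-pregnant and 30 post natal participants".
- Section 8.7 covers withdrawals: "If participants are withdrawn from the study they will be replaced and data acquired from withdrawn participants will be destroyed". The reason for withdrawal goes on the CRF.

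The terms *complete*, *spurious* and *evaluable* are not defined. No section says how a sample that has clotted before it reaches the analyser is to be recorded, scored, counted or reported. No sensitivity analysis is planned.

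Section 4 explains why clotting matters: if the valve activates the clotting cascade, "it could reduce the time the clinician has to utilise the blood before it clots in the syringe".

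**The concern.** R time can be measured only on blood that is still liquid when loaded. If one sample of a pair has already clotted, the participant has one R time and no difference. Under Sections 8.6 and 11.5 that is neither a paired test nor a complete data set, so another participant would be recruited in that place. A partly clotted sample with a very short R time could go the same way if someone judged it spurious.

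Such a loss carries information. It is the most extreme form of the effect that Section 4 worries about, and how often it happens may depend on the needle. A rule that recruits until enough measurable pairs exist then selects the pairs in which the blood stayed liquid. With no CRF field for the event, nobody could learn afterwards how often it happened or with which needle.

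**Working it through.** **1. The plan's own figure.** Section 11.2 requires 10 non-pregnant and 30 post natal participants for a 25% reduction in R time, with alpha 5% and power 80%. The SD of the paired difference, the mean R time and the sidedness are not given, so these sizes can be neither reproduced nor refuted. Solving backwards, with a two-sided test assumed, SD = 25·√n / (1.960 + 0.842), as a percentage of mean R:

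- n = 10: 25 × 3.162 / 2.802 = 28.2%; with the noncentral t, 25.1%.
- n = 30: 25 × 5.477 / 2.802 = 48.9%; with the noncentral t, 47.2%.

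The sample sizes therefore imply a paired SD of roughly 25% to 49% of mean R. I take log-ratio SDs of 0.3 and 0.5 as about that range. The conversion is rough.

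**2. Room for replacement.** The synopsis plans 50 participants, and Section 17 budgets 100 TEG tests, which is 100 / 2 = 50 pairs. The analysis uses 40. Up to 50 − 40 = 10 pairs (10 / 50 = 20%) could be replaced within the stated totals.

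**3. Effect on the observed reduction.** Everything here is an assumption except the 25%. Let the new-to-standard R-time ratio be lognormal with median 0.75 and log-SD s. Suppose that pairs with a ratio below c lose their new-needle sample to early clotting and are replaced. Then

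- share lost: p = Φ[(ln c − ln 0.75) / s];
- median ratio among the pairs kept: 0.75 · exp{s · Φ⁻¹[(1 + p) / 2]}.

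| c | s | (ln c − ln 0.75)/s | p | Φ⁻¹[(1+p)/2] | median ratio | observed reduction |
|---|---|---|---|---|---|---|
| 0.5 | 0.3 | −1.352 | 8.8% | 0.111 | 0.775 | about 22% |
| 0.5 | 0.5 | −0.811 | 20.9% | 0.265 | 0.856 | about 14% |
| 0.25 | 0.3 | −3.662 | 0.01% | 0.0002 | 0.750 | 25% |
| 0.25 | 0.5 | −2.197 | 1.4% | 0.018 | 0.757 | about 24% |

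The cut-off c drives the result, and the documents give no basis for choosing it.

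**4. Early clotting as the only effect.** Simulation: 2,000 trials per cell, two-sided signed-rank test at 5%, SD 25.2% (n = 10) and 47.2% (n = 30). The new needle clots a share of samples and all other pairs show no difference. At shares from 0 to 30%, complete pairs reject in about 4% to 6% of trials, which is the error rate. Ranking the clotted samples worst rejects in 7%, 14% and 25% (n = 10) and in 14%, 39% and 73% (n = 30) at shares of 10%, 20% and 30%. The shares are assumed.

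**The case against.** **The event is hypothetical.** Section 4 speaks only of a theoretical potential for activation. No section gives a rate of early clotting or a time from draw to loading, and near-patient testing should keep that time short. This stands: the size of the bias is unknown and may be zero.

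**The dropping is one reading.** Section 11.4 counts those who complete the study protocol, Section 11.7 refers to completing the intervention arms, and Section 9.1 describes participation as phlebotomy with the two needles. Someone who gave both samples could satisfy all three, and Section 11.5 says there will be no unused data sets. This stands in part, because the undefined terms leave room for it. But Section 8.6 counts paired TEG tests, and a paired R-time comparison has no value to use for such a participant. On either reading the event is not captured. If it were handled as a withdrawal, the data would be destroyed and only a CRF reason would remain, with no plan to report it by needle.

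**The direction is not fixed.** A reader might infer that the rule must favour the new needle. The documents do not support that. Section 4 has 12 ml drawn through the standard needle and 2 ml through the new one. If the larger draw takes longer, which is not stated, early clotting could fall on the standard needle and the bias would reverse.

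**The size is sensitive to its inputs.** A log-ratio SD of 0.7 with a cut-off of 0.5 would bring the observed reduction down to about 3%, but that SD lies above what the planned sample sizes imply. The model also treats all variation in the ratio as real activation. The punctures are in separate veins (Section 6.1), and assay and vein-to-vein noise does not clot a syringe. If half the log-ratio variance were noise (assumed), the observed reduction at cut-off 0.5 would be about 24% (SD 0.3) or 19% (SD 0.5).

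**Worst-rank scoring changes the question.** It turns a change in R time into a composite of R time and early clotting. This also stands, and is why the two analyses should be shown together.

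**Conclusion.** The point holds as a conditional one. The counting and replacement rules would very probably remove a pair in which a sample clots before loading, and the plan has no provision to record or report it by needle. That the sample gives no R time is an inference, though a plain one.

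With losses mainly on the new needle, the comparison moves towards no difference; with losses mainly on the standard needle, it moves the other way; with no early clots, nothing changes. On the assumptions in the working, a true 25% reduction would appear as about 22% to 14% (cut-off 0.5) or 25% to 24% (cut-off 0.25). These figures show a range from negligible to material and do not predict where this trial lies.

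A reader might infer that early clotting is the very event the trial sets out to detect, or that the plan is bound to pass a device that clots blood. Neither is supported. Section 5.1 seeks a difference in clotting values and Section 11.1 measures R time; clotting in the syringe is a possible consequence named in the background. The change should be made, because it is cheap and the information cannot be recovered later if it is not recorded.

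**What to change.** 1. In Sections 8.6 and 11.5, state that a sample visibly clotted in the needle, valve or syringe before TEG loading is an outcome, and is neither missing nor spurious. Define *complete*, *spurious* and *evaluable* before any data are seen.
2. Record the event on the CRF by needle and draw order, and keep that participant in the data.
3. Report the number of such samples per needle beside the R-time result.
4. Add a paired signed-rank analysis of all attempted pairs in each population, giving the clotted side the shortest R time and treating a pair with both sides clotted as a tie. Present it with the complete-pairs R-time analysis so that each shows what the other leaves out.

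The cost is a few sentences, one CRF tick-box per needle and one further analysis, with no additional participants. Worst-rank scoring need not create false positives: in a simulation with both needles clotting 10% of samples and no true difference, it rejected in 5.9% (n = 30) and 4.8% (n = 10) of trials at a nominal 5%. The small downside is that a clot caused by a slow or difficult draw counts against that needle; the complete-pairs analysis and the recorded draw order help to show this.

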8.4 Randomisation and Codebreaking (if applicable)

All participants will have a paired set of bloods taken with a hypodermic needle and the new one way valve filter needle. We will alternate which needle is used first between patients.

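### Sections 8.7 and 11.5 allow pairs to be removed and replaced without a criterion or concealment of the result; if removal depends on R time, the estimate can be biased either way and, under some rules, type I error rises

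*Combined protocol and SAP*

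**What the plan says.** Two separate rules remove pairs.

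- **Withdrawal (8.7).** "the investigator may discontinue a participant from the study at any time if the investigator considers it necessary for any reason". The listed reasons include significant protocol deviation and ineligibility discovered retrospectively, so withdrawal can follow the TEG result. Then: "If participants are withdrawn from the study they will be replaced and data acquired from withdrawn participants will be destroyed". One item is expressly kept: "The reason for withdrawal will be recorded in the CRF".
- **Spurious data (11.5).** "Spurious data will be excluded from analysis and will require additional recruitment". No criterion, decision-maker, timing or log is given. The sentence before it reads "There will be no unused data sets". Section 11.7 adds "All evaluable patient data will be analysed to a total of 10 non-pregnant and 30 post natal participants", and evaluable is not defined.

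On concealment, 8.4 offers only this: "We will alternate which needle is used first between patients". No section codes the samples or keeps needle or R time from whoever decides on withdrawal or exclusion. No sensitivity analysis of all pairs obtained is planned.

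**The concern.** The primary outcome is the within-participant change in R time (11.1). Under both rules a pair can leave the data set after its R times are known, on an unstated ground, and a new participant brings the count back to 10 or 30. The final data set then looks complete.

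The bias has no single direction. Section 4 gives activation of clotting by the valve as the reason for the study, so a very short R time on the valve needle is both the effect sought and a value that could be called spurious. Removing it would hide the effect. Removing a pair with a large increase would exaggerate it.

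With 10 and 30 pairs a single removal can matter. Where the data have been destroyed, a reader would have the stated reason but perhaps not the R times, and so could not judge whether the removal was related to the result.

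**Working it through.** **1. The plan's own figure.** Section 11.2 gives n = 10 and n = 30 for a 25% reduction, alpha 5% and power 80%. It cannot be reproduced, because neither the SD of the paired difference nor the mean R time is stated. Solving backwards, two-sided, with SD as a percentage of mean R:

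- Normal formula, SD = 25 × √n / (1.960 + 0.842): 28.2 for n = 10 and 48.9 for n = 30.
- Noncentral t, solved for 80% power: 25.1 for n = 10 and 47.2 for n = 30. These are used below.

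**2. Set-up.** Paired differences are normal with mean −25 (effect) or 0 (no effect) and the SDs above. Draw n + 1 pairs, remove one by a stated rule, and apply an exact two-sided 5% signed-rank test to the n that remain; 200,000 trials per case. Assumptions not in the documents: the test (11.1 says only paired and non-parametric), two-sidedness, and one removal per trial (no exclusion rate is given).

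**3. Results** (n = 10 / n = 30).

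| Pair removed | Mean reduction, true 25% | Power | Two-sided error, no effect |
|---|---|---|---|
| None, or at random | 25% / 25% | 78% / 78% | about 5% / 5% |
| Most shortened | 21.0% / 21.8% | 72% / 72% | 9.5% / 7.0% |
| Largest increase | 29.0% / 28.2% | 94% / 88% | 9.5% / 7.0% |
| Furthest from sample median | 25% / 25% | 85% / 80% | 12.0% / 8.2% |
| Furthest from zero | 21.1% / 22.2% | 73% / 74% | about 5% / 5% |

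When the most-shortened pair is removed, the excess error is mostly a false finding that R is longer (8.3% and 5.5% against a nominal 2.5%). When the largest increase is removed, it is mostly a false finding that R is shorter, of the same size.

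The mean shift can be checked by hand. It equals SD × (expected maximum of n + 1 standard normals) / n: 25.1 × 1.59 / 10 = 4.0 and 47.2 × 2.06 / 30 = 3.2, so 25 − 4.0 = 21.0 and 25 − 3.2 = 21.8.

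**4. The last two rows.** Both remove an outlier from either side. Judged against the other pairs, the removal raises the error and leaves the mean alone. Judged against zero, it leaves the error alone and attenuates the mean. The consequence depends on the rule, and the plan gives none.

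**5. Model check.** The normal model puts 5.6% of post natal pairs below −100%, which is impossible. A log-ratio model (SD 0.289 and 0.544) gives nearly the same results: 21.5% and 22.2% with the most-shortened pair removed, 28.4% and 27.8% with the largest increase removed, and error of 12.0% and 8.1% for the furthest from the median.

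**6. How often a pair is removed.** The table forces a removal in every trial. If a pair is replaced only when it lies beyond 3 interquartile ranges from the quartiles, the error is about 5.8% and 5.0%. At 1.5 interquartile ranges it is about 8.3% and 6.3%.

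**The case against.** Participation ends at the TEG test (6.1, 8.5) and the synopsis lists no follow-up, so ordinary dropout after the result is unlikely. This stands. The exposure is investigator-led or retrospective withdrawal, and the spurious-data rule.

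The table forces a removal even when no pair looks odd. This also stands: its figures are upper-end cases for a single removal, and a strict outlier rule does little harm to the error rate.

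Destroying data may be meant to respect withdrawn consent. But 8.7 applies it to every withdrawal, including those the investigator initiates.

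A reader might draw four stronger conclusions that the documents or the figures do not support:

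- *Any result-related removal takes the error above 5%, or removing outliers on both sides must do so.* Removal by distance from zero leaves it at about 5%.
- *Withdrawn participants' R times cannot be checked.* Section 8.7 does not say whether the destroyed data include source records or analyser output. Section 8.8 distinguishes source documents from CRF data, and the monitoring in section 13 could come before destruction. They may be unavailable; no more can be said.
- *Adverse event data will be lost.* Section 10.2 requires all AEs on the CRF, 10.3 sends SAE forms to the sponsor, and 8.7 itself says "If the participant is withdrawn due to an adverse event, the investigator will arrange for follow-up visits or telephone calls". The destruction sentence makes no exception for these records, but this is an ambiguity of wording.
- *The sentence on unused data sets contradicts the exclusion rule.* It may mean only that recruitment stops at 40 with no surplus. It needs clarifying.

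Nor do the documents suggest that anyone intends to remove pairs because of their results.

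**Conclusion.** The point holds in conditional form and should be fixed. The plan has a stated destroy-and-replace rule and a stated exclude-and-replace rule without a criterion, and nothing separates either decision from needle or R time. Removal unrelated to R is harmless. Removal related to R can move a true 25% reduction to about 21% or 29% with 10 pairs, and to about 22% or 28% with 30. Depending on the rule, two-sided error stays near 5% or rises to about 12% and 8%. These sizes rest on back-solved SDs, an assumed two-sided signed-rank test and one removal in every trial; they illustrate and do not predict. The case for change rests on the wording of 8.7, 11.5 and 11.7, not on the simulated figures.

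**What to change.** 1. **Section 8.7.** Replace destruction with retention and reporting of data collected up to withdrawal, unless the participant withdraws consent to their use. State that AE records are kept, in line with 10.2.
2. **Sections 11.5 and 11.7.** Define spurious and evaluable. Limit exclusion from the analysis to pre-specified technical faults of the TEG run or labelling, decided where practicable from a coded sample before R is seen. State that an R time is not by itself a ground for exclusion. Reconcile this with the clotting-abnormality exclusion in 7.3, the laboratory clotting tests in 6.2 and retrospective ineligibility in 8.7, so that an ineligibility decision does not use the study R time. Clarify the sentence on unused data sets.
3. **Reporting.** Log and report every exclusion and withdrawal by needle and reason. Add a sensitivity analysis of all pairs obtained, subject to consent, in which a sample that clotted before analysis is ranked as the shortest R time. Omitting such samples would bring back the attenuation.

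Cost: a protocol amendment with the approvals in 14.5 and any matching consent wording, a simple sample code, a log and one extra analysis. No extra participants.

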11.6 Procedures for Reporting any Deviation(s) from the Original Statistical Plan

We don't anticipate any variation from our statistical plan, however this would be explained in the final report if required.

11.7 Inclusion in Analysis

All evaluable patient data will be analysed to a total of 10 non-pregnant and 30 post natal participants have completed the intervention arms of the study.

12. DIRECT ACCESS TO SOURCE DATA/DOCUMENTS

Direct access will be granted to authorised representatives from the sponsor, host institution and the regulatory authorities to permit trial-related monitoring, audits and inspections.

